8. EFFICACY

Changes from baseline for efficacy data will be calculated as the post-treatment value minus the corresponding defined baseline (see Section 6.2.1). Descriptive summaries will be presented for observed and change values by treatment and visit. Assessment of proportion data will be presented by frequency and proportion by treatment and visit.

8.1. STUDY 603A

For all analyses at Week 12, LOCF will be used for subjects who lack Week 12 assessments or who require intensification of anti-hypertensive therapy. Only post-baseline values before rescue medication will be carried forward.

8.1.1. Primary Efficacy Endpoint and Analysis

The primary efficacy endpoint is the change from baseline to week 12 of the 24-hour mean ambulatory SBP in the bexagliflozin group compared to the change in the placebo group, testing for superiority at a two-sided 0.05 level of significance. A valid ABPM reading will require:

- ≥ 64 BP total readings; and
- ≥ 51 BP daytime readings or ≥ 13 BP nighttime readings.

Only valid ABPM will be used for analysis.

8.1.1.1. Primary Efficacy Analysis

Let $\mu_{\text{Bexagliflozin}, 12}$ and $\mu_{\text{PBO}, 12}$ represent the mean changes from baseline in 24-hour ambulatory SBP at Week 12 for bexagliflozin and placebo arm, respectively. The following hypotheses will be tested:

$$H_0: \mu_{\text{Bexagliflozin}, 12} = \mu_{\text{PBO}, 12} \text{ versus } H_1: \mu_{\text{Bexagliflozin}, 12} \neq \mu_{\text{PBO}, 12}$$

To test this hypothesis, an analysis of covariance (ANCOVA) will be applied to analyze the mean change in 24-hour average ABPM SBP. The ANCOVA model will include terms for diabetes status (history of type 2 diabetes mellitus [T2DM] or not), renal function (eGFR at screening as continuous variable), pre-treatment status (presently medicated for hypertension or not), randomized treatment, and the baseline 24-hour mean SBP as fixed effect covariates. Change from baseline will be the dependent variable. Analysis will be conducted on ITT analysis set. The last ABPM SBP post baseline will be used for the analysis.

Descriptive statistics (n, mean, Q1, median, Q3, SD, minimum, and maximum) will be reported by treatment group, along with the least squares means, differences between LS means, a 2-sided 95% confidence interval (CI) for each difference, p-value from the model effects.

8.1.1.2. Sensitivity Analysis

Sensitivity analyses will be conducted to examine the robustness of the inference:

- If subject receives rescue medication and has an ABPM value after rescue medication, this value will be analyzed as an outcome. In study 603A, a subject who requires rescue medication will attempt to complete an ABPM before initiating rescue medication. A subject will be terminated if rescue medication starts within the first 6 weeks, or will start study 603B (after the first 6 weeks). No post-rescue medication value is expected and as a result, analysis of post-rescue data will not be conducted. This sensitivity analysis will only be conducted if >5 subjects have post rescue medication values.
- Subjects without scheduled Week 12 assessment (i.e., post baseline ABPM for subjects who did not complete 12 weeks treatment) will be excluded from the analysis.
- A tipping point analysis will be conducted for subjects without Week 12 assessments. The following steps will be taken:
 - If subject has withdrawn from the study or has initiated rescue medication, the value will be considered as missing.
 - A regression model will be used to impute the missing change value using SAS PROC MI procedure. Covariate will include baseline 24-hr mean SBP, diabetes status (history of T2DM or not), renal function (eGFR at screening), pre-treatment status (presently medicated for hypertension or not) and randomized treatment. One hundred datasets will be imputed.
 - If subjects with missing values are in the placebo treatment arm, the imputed value will be used in the analysis.
 - If the subject is in the bexagliflozin treatment arm, a series of δ mm Hg will be added to the imputed values. The δ value will range from 0.5 to 5, with step size of 0.5.
 - The same ANCOVA analysis from Section 8.1.1.1 will be conducted for each imputed dataset and δ . The results will be combined using PROC MIANALYZE in SAS.
- Wilcoxon rank sum test will be conducted including all post baseline ABPM SBP values. For a subject who has no post baseline assessment, the worst outcome within the treatment group (i.e., change from baseline = the maximum increase from baseline in the same treatment group) will be considered.

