3.7. DETERMINATION OF SAMPLE SIZE

The primary efficacy endpoint of study 603A is the change from baseline (Day 1) to week 12 in the 24-hour average SBP of the bexagliflozin group compared to the placebo group using superiority testing at an overall two-sided 0.05 level of significance.

The primary efficacy endpoint of study 603B is the change from week 12 to week 24 in the 24-hour average SBP in the bexagliflozin group compared to the placebo group using superiority testing at an overall two-sided 0.05 level of significance.

Although the patient population was anticipated to be nearly identical between the two studies, they were to be carried out as independent investigations with respect to their individual primary and secondary endpoints. The assumptions used to estimate the sample size for the primary endpoint of study 603A were:

1. The magnitude of the decrease from baseline (Day 1) to week 12 of the 24 h mean SBP in the bexagliflozin treatment arm will exceed that found in the placebo arm by 5 mm Hg;
2. The standard deviation of the change from baseline to week 12 will be 15 mm Hg for both the active and placebo groups;
3. The two-sided significance level is 0.05.

The assumptions to estimate the sample size required for the primary endpoint of study 603B were:

1. Bexagliflozin will remain effective for at least 24 weeks. The 24-hour average ABPM SBP will not change between Week 12 and Week 24.
2. Subjects who are randomized to receive placebo will show an increase in ABPM SBP of 4 mm Hg between Week 12 and Week 24.
3. The standard deviation of the change is 15 mm Hg for both the active and placebo groups.
4. The two-sided significance level is 0.05.

A sample size of 254 per arm is required for the measurement to have 85% power to attain significance for the second primary endpoint. It is estimated that 75% of subjects will have completed the 36 weeks of study treatment since the first randomization. Thus a total sample size of 680 subjects is planned for the first randomization. It is estimated that approximately 8% will drop out for the first 12 weeks. A sample size of 626 subjects at the end of the first 12 weeks will provide >95% power for the first primary endpoint.

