3.10. STUDY PROCEDURES AND FLOWCHART

The activities that must be performed at each clinic visit listed below are presented in Table 1.

A visit window of ± 3 days is allowed for all post-randomization visits. Visit 3 is the day of randomization and the basis for the visit window. A repeat ABPM shall be performed within 2 days if the 24h-ABPM is incomplete. Only the second set of ABPM data will be entered in the case report form on visits 2-3, 5-6, 8-9, and 10-11. The other specified procedures in the same assessment period do not need to be repeated. If the ABPM fails twice at visit 3 prior to randomization, the subject is considered a screen failed subject. If the ABPM cannot be completed successfully twice after randomization, the ABPM BP for that assessment period is considered missing.

Procedures listed for visit 10 and 11 will be completed if a subject is withdrawn from the study.

Table 1 Schedule of Events

Procedures	Screening/ Run-in		Study 603A			Study 603B					
			Weeks 1 to 12			Weeks 1 to 12			Week 13 to 24		
Cumulative study week			1-12			13-24			25-36		
Visit Number	1	2	3	4	5	6	7	8	9	10	11
Time to first randomization	-13 or -12 d	-1d	0w +1d	6w	12w	12w +1d	18w	24w	24w +1d	36w	36w +1d
Informed Consent	x										
Medical History	x										
Inclusion/Exclusion Criteria	x	x	x								
Run-in drug dispensation	x										
Randomization			x						x		
Begin 24-h ABPM		x			x			x		x	
End 24-h ABPM			x			x			x		x
Double blind drug dispensation			x			x			x		
Whole blood sample	x	x			x			x		x	
Hematology	x	x			x			x		x	
HbA1c	x	x			x			x			
Serum sample										x	
Chemistry	x	x			x			x		x	
Lipids	x	x			x			x		x	
Urine sample											
Urinalysis	x	x			x			x		x	
Pregnancy test (WCBP)	x	x			x			x		x	
Population PK Sampling							x	x			
12-Lead ECG	x	x			x			x		x	
Vital Signs	x	x	x	x	x	x	x	x	x	x	x
Abbreviated PE & weight	x				x			x		x	
Complete PE & weight		x									
Adverse Events Assessments		x		x	x		x	x		x	x
Concomitant Medication Assessments		x		x	x		x	x		x	x

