8.2.1.2. Sensitivity Analysis

- If subject has received rescue medication and has an ABPM value after rescue medication, this value will be analyzed as an outcome. Per protocol, if subject requires rescue medication, ABPM will be taken before starting rescue medication. In such case, ABPM is not normally measured again after rescue medication. This sensitivity analysis will only be conducted if >5 subjects have post rescue medication values.
- Subjects without scheduled Week 24 assessments will be excluded from the analysis.
- A tipping point analysis will be conducted if there are subjects missing Week 24 assessment. Steps below will be followed:
 - If subject used rescue medication or discontinued during withdrawal period, value will be considered as missing.
 - A regression model will be used to impute the missing change value using SAS PROC MI procedure. Covariate will include baseline 24-hr mean SBP, the treatment group stratification by response as assessed by ABPM SBP at baseline (Week 12), and randomized treatment for study 603B. One hundred datasets will be imputed.
 - If subjects with missing value are in the placebo treatment arm, the imputed values will be used.
 - If the subject is in the bexagliflozin treatment arm, a series of δ will be added to the imputed values. The δ value will range from 0.5 to 5, with step size equals 0.5.
 - Same ANCOVA analysis from Section 8.2.1.1 will be conducted for each imputed dataset and δ . Results will be combined using PROC MIANALYZE in SAS.
- Wilcoxon rank sum test will be conducted including all Week 24 ABPM SBP values. If subject requires rescue medication, ABPM before starting rescue medication will be used; for a subject who has no post baseline assessment, the worst outcome within the treatment group (i.e., change from baseline = the maximum increase from baseline in the same treatment group) will be considered.

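### The tipping-point analyses stop at δ = 5 mm Hg, with no δ = 0 row and no rule to continue, so most significant results would read only as tipping above 5

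*SAP*

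**What the plan says.** SAP 8.1.1.2 (603A) imputes missing changes by regression, 100 times. It leaves the placebo imputations as they are and adds δ mm Hg to the bexagliflozin imputations: "The δ value will range from 0.5 to 5, with step size of 0.5". SAP 8.2.1.2 (603B) does the same: "The δ value will range from 0.5 to 5, with step size equals 0.5". The protocol gives the same range in the Synopsis and in section 9.5. Neither document lists δ = 0 or asks for values beyond 5, and SAP section 12 does not alter the grid.

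What is imputed goes beyond dropout. For 603A: "If subject has withdrawn from the study or has initiated rescue medication, the value will be considered as missing". For 603B: "If subject used rescue medication or discontinued during withdrawal period, value will be considered as missing". Failed recordings add to this (SAP 3.10): "If the ABPM cannot be completed successfully twice after randomization, the ABPM BP for that assessment period is considered missing".

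Each study also has an analysis restricted to subjects with the scheduled visit. For 603A: "Subjects without scheduled Week 12 assessment (i.e., post baseline ABPM for subjects who did not complete 12 weeks treatment) will be excluded". For 603B: "Subjects without scheduled Week 24 assessments will be excluded from the analysis". A Wilcoxon test gives the worst change in the subject's own arm to anyone with no post-baseline value.

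**The concern.** A tipping-point analysis is meant to show how badly unobserved active-arm subjects would have to fare before the conclusion changes. If every row on the grid is still significant, the report can say only that the value lies above 5. That does not separate a result that tips at 6 from one that tips at 30.

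This is the only planned ANCOVA-based analysis that varies the missing-data assumption over a range. The restricted analysis and the Wilcoxon test each make one fixed assumption. The post-rescue analysis runs only if more than 5 subjects have such values, and SAP 8.1.1.2 expects none in 603A. Extending the grid after unblinding would look data-driven.

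**Working it through.** **Inputs (SAP 3.7).** SD 15 in both studies; effects 5 (603A) and 4 (603B); two-sided 0.05; 680 randomized 1:1; 254 per arm needed in 603B; 75% completing 36 weeks. On 603A dropout: "It is estimated that approximately 8% will drop out for the first 12 weeks".

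**The plan's own figures.** For 603B, n = 2(1.960 + 1.036)² × 15²/4² = 252.5, or 253 per arm by normal approximation. The noncentral t gives 84.9% power at 253 and 85.1% at 254, so 254 reproduces. 508/0.75 gives 678, against 680 planned. 680 × 0.92 = 626, or 313 per arm, which gives 98.6% power in 603A, consistent with the stated figure above 95%.

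**Assumed input.** Dropout within the 603B withdrawal period is not stated. Even proportional loss from 92% at week 12 to 75% at week 36 gives 1 − √(0.75/0.92) = 9.7%, taken as 10%. If all of that loss fell in the withdrawal period it would be 1 − 0.75/0.92 = 18.5%. No rescue rate is given, so up to 30% missing is shown.

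**Method.** Let f be the missing fraction and n the completers per arm.
- SE = 15√(2/n).
- Shift at δ = 5 is 5f.
- SE at δ = 5 is √(SE² + 25f(1−f)/N), with N = n/(1−f).
- A significant result tips within the grid if the completer difference lies between 1.96·SE and 1.96·SE(δ=5) + 5f.
- Share tipping = P(difference in that band)/P(significant).

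**603A, effect 5, f = 8%, n = 313.** SE = 1.199 and shift = 0.40. The band runs from 2.35 to 2.75 (p from 0.05 down to 0.022). Probability of significance is 98.6% at δ = 0 and 96.9% at δ = 5. Share = 1 − 0.969/0.986 = 1.7%.

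**603B, effect 4, f = 10%, n = 254.** SE = 1.331 and shift = 0.50. The band runs from 2.61 to 3.11 (p from 0.05 down to 0.019). Probability of significance is 85.2% at δ = 0 and 74.7% at δ = 5. Share = 1 − 0.747/0.852 = 12.3%.

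**Other missing fractions.** Ranges run from n held at the planned completers to n reduced by the extra loss.

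| Study, true effect | f | Share tipping by δ = 5 |
|---|---|---|
| 603A, 5 | 20% | 7.3% (n = 313) to 10.2% (n = 272) |
| 603A, 5 | 30% | 15.9% (n = 313) to 24.7% (n = 238) |
| 603A, 3 | 20% | 47% (n = 272) |
| 603A, 2 | 20% | 66% (n = 272) |
| 603B, 4 | 20% | 28.1% (n = 254) to 30.4% (n = 226) |
| 603B, 4 | 30% | 45.5% (n = 254) to about 50% (n = 198) |

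**Where the tipping value lies.** This was simulated with the SAP's imputation covariates, 100 imputations and Rubin's rules, on 200 datasets per scenario. There were 340 per arm in 603A and 282 in 603B, with equal random missingness by arm and the completer difference fixed at the design effect. Covariate distributions were assumed: T2DM 25%, mean eGFR 80, medicated 80%, and 603B response strata 30/40/25/5%. Median tipping δ (range):

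| Study | Missing | Median tipping δ (range) |
|---|---|---|
| 603A | 8% | 32.0 (29.5–35.0) |
| 603A | 20% | 12.5 (11.0–14.0) |
| 603A | 30% | 8.0 (6.5–9.0) |
| 603B | 10% | 14.0 (10.5–17.0) |
| 603B | 20% | 6.5 (4.5–8.0) |
| 603B | 30% | 3.5 (2.5–5.0) |

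Only the last median lies inside the grid. A second simulation, without covariates and with 1,500 trials per scenario, left 98% of significant 603A results (8% missing) and 89% of significant 603B results (9.7% missing) still significant at δ = 5.

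**The missing δ = 0 row.** In 603A at 8% missing, δ = 0 differed from the completer ANCOVA by 0.03 mm Hg on average (maximum 0.09), and both had SE 1.181.

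**The case against.** A bounded grid is a legitimate pre-specified choice, and this ceiling is not arbitrary. It equals the 603A design effect and exceeds the 603B one, so at δ = 5 the imputed active-arm subjects get none of the assumed benefit. Remaining significant there is an interpretable finding. This stands, and it is why every planned δ should be kept.

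The estimate is linear in δ, so a reader could extrapolate. The straight line (effect − 1.96·SE)/f gives 33.1, 12.4 and 7.7 in 603A, against simulated 32.0, 12.5 and 8.0. In 603B it gives 13.9, 6.2 and 3.5, against 14.0, 6.5 and 3.5. The recovery is good, to about 1 mm Hg. But the plan does not ask for it, and it needs the standard errors and the missing fraction to be reported alongside.

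A tipping value near 32 is clinically remote, and a reader might conclude the same from robustness at 5. That is fair for 603A at 8% missing, less so for 603B, where the value could be about 6 or 14. The grid also works better for fragile results, as the rows for true effects 3 and 2 show.

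The δ = 0 complaint is the weaker part. In 603A the restricted analysis, run with the same ANCOVA, nearly supplies it. In 603B the match is looser, because rescued subjects continue the study and may attend the scheduled visit, yet the tipping-point analysis sets them to missing.

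**Conclusion.** The concern holds. At the design effects, with planned dropout in 603A and 10% missing assumed in 603B, about 98% and 88% of significant results would still be significant at δ = 5. The analysis would then not deliver the value it is named for. In 603B most significant results go unresolved until the missing fraction, rescue included, reaches roughly 30%. The statement reverses where a small true effect meets heavy missingness.

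The 603A figure rests on documented inputs plus the assumption that missingness equals planned dropout. The 603B figure rests on an assumed withdrawal-period loss. Rescue and failed recordings could raise both fractions, and their rates are not given. The primary analysis, error rates and sample size are untouched. This is a change that should be made, not a threat to validity.

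**What to change.** In SAP 8.1.1.2 and 8.2.1.2, keep all ten planned values and add δ = 0. If that result is significant, increase δ in steps of 0.5 until the two-sided p-value exceeds 0.05. Report that δ and the number imputed per arm, beside the observed mean ABPM change in rescued and withdrawn subjects who have a valid recording, so that readers can judge plausibility. The rule works at any missing fraction, so rescue and dropout need not be forecast. List it in SAP section 12 as a change from protocol 9.5, before unblinding.

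Optional, and mainly for 603B: one further run that keeps valid pre-rescue ABPM values, as the primary analysis does, and imputes only subjects with no such value.

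The cost is SAP wording and a longer loop in the planned PROC MI/MIANALYZE program, plus one run if the optional version is taken. No patients, visits or procedures are added.

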8.1.2. Secondary Efficacy Endpoints and Analyses

The secondary efficacy endpoints include mean ambulatory and seated office SBP, mean ambulatory and seated office DBP. Secondary efficacy endpoints will be accessed without multiplicity adjustment. Analyses will be primarily based on ITT analysis set.

8.1.2.1. The proportion of subjects who achieve a reduction of mean ambulatory SBP of 10 mm Hg or greater

Subjects who achieve a reduction of mean ambulatory SBP of ≥ 10 mm Hg will be summarized using frequency and percentage by treatment arm. Logistic regression will be used to analyze the treatment effect. The model will include diabetes status (history of T2DM or not), renal function (eGFR at screening as continuous variable), pre-treatment status (presently medicated for hypertension or not), baseline mean

ambulatory SBP value and randomized treatment. The LS Mean responding proportion and 95% CI will be estimated within each treatment group from a logistic regression model. A p-value for comparison by treatment group will also be provided. Two different outcomes will be explored:

- Responder will be defined using the last-post baseline value. If a subject received rescue medication, the value prior to the initiation of rescue medication will be used (primary analysis);
- Subjects with no post baseline assessments prior to early withdrawal from the study or initiation of the rescue medication will be considered as non-responders (sensitivity analysis).

8.1.2.2. The proportion of subjects who achieve ambulatory SBP of 135 mm Hg or less

The summary and analyses will be provided as in section 8.1.2.1.

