12. CHANGE FROM ANALYSIS PLANNED IN PROTOCOL

Wilcoxon rank sum tests were added to both primary endpoints as sensitivity analysis.

Protocol specified that if < 64 BP readings (51 day time and 13 night time BP readings) are recorded, ABPM is considered as invalid and is repeated. In SAP, the validity criteria has been relax to include more subjects (section 8.1.1.1).

Additional exploratory endpoints are added in sections 4.1.3 and 4.2.3.

Baselines for efficacy endpoints are defined as the last measurement prior to the first dose of double-blind study medication, not prior to randomization per protocol. Randomization date is only used if subject is not dosed.

Adverse events occurred during 603B run-in period will not be summarized separately as stated in the protocol, instead, adverse events occurred during bexagliflozin treatment period will be summarized based on integrated safety analysis set. Some tables are only prepared for integrated safety analysis set due to lack of event occurrences.

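### Both Wilcoxon sensitivity tests give a subject with no post-baseline ABPM the worst value of his or her own arm, so the same event is scored by arm and tends to rank better on bexagliflozin.

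*SAP*

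**What the plan says.** SAP section 12 records that "Wilcoxon rank sum tests were added to both primary endpoints as sensitivity analysis". For 603A, section 8.1.1.2 states that a "Wilcoxon rank sum test will be conducted including all post baseline ABPM SBP values". A subject with none is given "the worst outcome within the treatment group (i.e., change from baseline = the maximum increase from baseline in the same treatment group". Section 8.2.1.2 repeats the rule for 603B: "for a subject who has no post baseline assessment, the worst outcome within the treatment group (i.e., change from baseline = the maximum increase from baseline", again taken from the subject's own arm. Neither section sets a value or rank common to both arms, and section 12 gives no reason for the within-arm choice.

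The responder sensitivity analysis in SAP 8.1.2.1 handles the same event without regard to arm: "Subjects with no post baseline assessments prior to early withdrawal from the study or initiation of the rescue medication will be considered as non-responders".

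Two other statements bear on how often the rule is used. SAP 3.7 says "It is estimated that approximately 8% will drop out for the first 12 weeks". SAP 3.10 says "Procedures listed for visit 10 and 11 will be completed if a subject is withdrawn from the study", and those visits include a 24-hour ABPM.

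**The concern.** When a rank test gives missing subjects a worst outcome, the same event should receive the same score in either arm. Otherwise the score carries treatment information that has nothing to do with the missing subject. Here the penalty comes from the arm's own results, so the better the drug works, the milder the penalty on its missing subjects tends to be.

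There is a second effect when the drug does nothing. One arm will by chance hold the higher maximum, and every imputed subject in that arm then ranks above every imputed subject in the other. The rank-sum variance does not allow for this block ordering.

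The 603A primary analysis carries forward only post-baseline values (SAP 8.1), so a subject with none contributes nothing to it. Of the listed sensitivity analyses, only the tipping-point and Wilcoxon analyses bring such subjects back, and only the Wilcoxon assigns them a worst outcome. A softened penalty weakens that check.

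**Working it through.** **Inputs from SAP 3.7.** SD of change 15 mm Hg in each arm; effect 5 mm Hg in 603A and 4 mm Hg in 603B; two-sided 5% level; 680 randomized, so 340 per arm; 8% loss by week 12; 75% completing 36 weeks; 254 per arm needed in 603B.

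**The plan's own figures reproduce.** For 4 mm Hg, SD 15 and 85% power the calculation gives 253 per arm (254 stated); 254 per arm gives 85.2% power. 508/0.75 = 677.3, so 678 (680 stated). 680 × 0.92 = 625.6 (626 stated). With 313 per arm and 5 mm Hg, power is 98.6% (>95% stated). The documents give no figure for the Wilcoxon tests.

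**Assumptions not in the documents.** Normal changes; missingness unrelated to outcome, at the same rate in both arms but with the count in each arm varying by chance (binomial); the missing shares themselves; and the 603B arm size. SAP 3.7 implies between 254 and 626/2 = 313 per arm at the second randomization, so later loss lies between 0 and 1 − 254/313 = 19%. The midpoint, about 284, implies roughly 10% loss.

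**Which maximum is lower.** Under the planned effects the bexagliflozin maximum is below the placebo maximum in about 74% of 603A trials and about 70% of 603B trials.

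**Size by hand.** Let *m* subjects be imputed in each of two arms of *n*. Under a common worst rank all 2*m* are tied. Under the own-arm rule the block with the higher maximum moves up *m*/2 ranks on average and the other moves down *m*/2, ignoring observed values lying between the two maxima. Each arm's rank sum therefore moves by *m*²/2, against a standard deviation of √(*n*²(2*n*+1)/12).

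- 603A, *n* = 340, *m* = 27 (8%): 27²/2 = 364.5; √(340² × 681/12) = 2561; shift in Z = ±0.14.
- 603B, *n* = 284, *m* = 28 (10%): 28²/2 = 392; √(284² × 569/12) = 1956; shift in Z = ±0.20.

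The shift grows with the square of the number missing, so it is negligible at a few percent and rises quickly after that. In 603A the direction favours bexagliflozin 74% of the time, so the net gain in mean Z is about (0.74 − 0.26) × 0.14 = 0.07. Simulation gives 0.09, because observed placebo values above the bexagliflozin maximum add a little.

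**Simulation, planned effect** (tie-corrected rank sum, 40,000 trials per setting):

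| Setting | Missing | Own-arm power | Common-rank power | Verdict differs |
|---|---|---|---|---|
| 603A, 340/arm | 8% | 95.2% | 94.6% | 1.8% |
| 603B, 284/arm | 5% | 80.0% | 79.4% | 1.9% |
| 603B, 284/arm | 10% | 73.4% | 70.6% | 8.0% |

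Mean Z in 603A is 3.90 v 3.87 at 4% missing and 3.65 v 3.56 at 8%. The last column counts changes in either direction; the net effect is the difference in power.

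Unequal missingness widens the gap. With 40 of 340 missing on bexagliflozin and 14 of 340 on placebo in 603A, a significant result favouring bexagliflozin occurs in 50.1% of trials under the own-arm rule, against 45.9% when all missing subjects get the larger of the two maxima.

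**Simulation, no effect** (100,000 trials per setting; 60,000 at 313 per arm). Type I error under the own-arm rule:

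- 340/arm: 5.0% at 2% missing, 5.2% at 4%, 5.5% at 8%.
- 284/arm: 5.1% at 5%, 6.0% at 10%.
- 313/arm: 8.8% at 15%.

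The common rank stays at 4.9–5.2% throughout.

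**The case against.** **Few subjects may reach the rule.** Withdrawn subjects are to have an exit ABPM, and subjects needing rescue are to have one beforehand, so the share with no ABPM should fall below dropout; recordings that fail twice push it up. The 8% case for 603A treats every planned dropout as having no ABPM. At 4% the two rules are almost indistinguishable. This stands, and it limits the size in 603A.

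**The type I result depends on the missingness model.** With counts fixed and equal in both arms (340 per arm, 8%), the null rejection rate is about 3.1% under the own-arm rule and 2.6–2.8% under a common rank, both below 5%. This is correct, but counts that vary between arms are the more natural model, and the own-arm rule has the higher rate under either. Because the inflation is symmetric, it is a separate defect and does not support the claim of favouring bexagliflozin.

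**The high-loss 603B cases are extremes.** 313 per arm at the second randomization means no loss during the 12-week active run-in. The upper limit, 19% with no exit ABPMs, gives 14.3% type I error; it is a bound, not an expectation.

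**The plan does not contradict itself, and other analyses cover the risk.** The SAP never calls this a worst-rank test, and a binary responder endpoint has only one failure value, so the responder rule cannot show that another rule was intended here. The tipping-point analysis penalises only bexagliflozin, by up to 5 mm Hg. No decision rule rests on the Wilcoxon p-value. All of this stands. It lowers the stakes but gives no reason to score the same event by arm.

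**Conclusion.** The concern holds. Both Wilcoxon tests score the same event by arm and, if the drug works as planned, usually in bexagliflozin's favour. This is a tendency: the direction reverses in roughly 26% of 603A trials and 30% of 603B trials, and with no effect and equal missingness neither arm is favoured on average.

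With equal missing rates, the gain in power is about 0.6 points in 603A at 8% missing (95.2 − 94.6) and 2.8 points in 603B at 10% with 284 per arm (73.4 − 70.6). Type I error in those settings is 5.5% and 6.0%. These sizes rest on assumed missing shares, normal changes, missingness unrelated to outcome, binomial counts and an assumed 603B arm size. The arm-dependent scoring itself follows from the SAP wording alone.

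This should be corrected, but it touches only supplementary analyses. The primary ANCOVA results do not change.

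**What to change.** In SAP 8.1.1.2 and 8.2.1.2, replace the own-arm maximum with one common worst rank: every subject with no post-baseline ABPM is tied with all other such subjects in both arms and ranked worse than the largest increase observed in either arm. Report the number imputed per arm beside each p-value, so the reader can see how much the result depends on the rule.

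The change is one phrase in two bullets and one line of code, with no new data or design change. The cost is a slightly less favourable sensitivity result if the drug works: power of about 94.6% instead of 95.2% in 603A at 8% missing, and 70.6% instead of 73.4% in 603B at 10%.
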